Meal detection will be enabled for the study. If iPancreas does not auto-detect the meal after 30 minutes of when they start eating, the study coordinator will assist the participant to enter a meal with a reduction to the amount of carbs entered based on the amount of time since the meal occurred, at the investigator's discretion. Participants will complete a pictorial nausea rating scale for reported nausea at study start and at approximately 6 hours after the first and second meal to report the worse nausea/vomiting they experienced over the prior 6 hours (the Baxter Retching Faces [BARF] scale) (see Protocol Appendix D)[78] and the approximate duration of the nausea.

The MPC closed loop system with the meal detection algorithm can detect if a meal has been eaten, estimate the grams of carbohydrates consumed then dose an insulin bolus based on the estimated grams of carbs, user's carb ratio and estimated time since the meal was consumed. The bolus is delivered automatically. The system reduces the bolus (per calculation below) by 25% as the detection occurs on average 25 minutes after meal is consumed.

$$Bolus(units) = \frac{\text{estimated carbohydrates (g)}}{\text{carb ratio } (\frac{g}{unit})}$$

If CBG >300mg/dL before the lunch meal, then the study will be stopped early and the participant will be given the option to return on a different day for the second meal.

The meal detection algorithm can be enabled or disabled through the insulin profile settings for a given time period. In order to avoid a meal detection before the two scheduled meals, the meal detection algorithm will be disabled through the insulin profile in between the meals.

If stopping criteria for hyperglycemia is reached, the study investigator will calculate a meal bolus with correction dose as in the equation below if no meal bolus was given by the system, otherwise, the investigator will calculate a correction bolus based on current glucose, target

glucose, and correction factor. The final dose that is delivered to the participant will be adjusted if needed by a study investigator considering insulin-on-board, time since meal consumption, and CGM trend. The Omnipod site will be assessed to determine if the insulin should be delivered via the Omnipod, syringe, or via the participant's own insulin pump after it is reconnected.

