	Women ≥ 19 yr	$354 - (6.91 * \text{age}) + \text{PA} * (9.36 * \text{wt} + 726 * \text{ht})$	PA=1 if sedentary PA=1.12 if low active PA=1.27 if active PA=1.45 if very active

BMI>25 Overweight/obese	Men ≥ 19 yr for Weight maintenance	1086- (10.1*age)+PA*(13.7*wt+416*ht)	PA=1 if sedentary PA=1.12 if low active PA=1.29 if active PA=1.59 if very active
	Women ≥ 19 yr for Weight maintenance	448- (7.95*age)+PA*(11.4*wt+619*ht)	PA=1 if sedentary PA=1.16 if low active PA=1.27 if active PA=1.44 if very active

[82]

Protocol Appendix D: Pictorial Nausea Rating Scale (the Baxter Retching Faces [BARF]/VAS scale)[78]

Investigative Site Instructions: The participant should complete the BARF/VAS for nausea/vomiting discomfort at approximately 6 hours after the first meal (prior to second meal) and six hours after the second meal (prior to discharge) to indicate the worse nausea/vomiting discomfort they have had over the prior 6 hours. Instruct the participant that the facial expressions represent the nausea severity they are experiencing. The face starts as neutral (shown below), but the animation becomes more nauseated as you proceed from 0 to 10.

[figure not shown]
The participant completes the VAS by drawing a single vertical line through the scale corresponding to the perceived intensity (severity) of discomfort matching the facial scale. The goal is for the subject to report the amount of discomfort, if any, remaining at each time point.

Note: If a subject is unable to physically complete the questionnaire, the subject will indicate the point on the VAS corresponding to their level of discomfort, and study staff will enter a vertical line at that point. Documentation will be provided on each completed questionnaire as to who completed the form.

Please verify the length of the VAS line to be 100-mm before providing it to the subject.

Subject Instructions: Discomfort could include cramping, abdominal pain, nausea or vomiting. The further to the right you make indicate, the more intense discomfort you are feeling.

You should normally draw a straight line across the scale to indicate your maximum level of discomfort over the prior 6 hours. However, if you felt no discomfort, you should circle the vertical line on the left end of scale (above the word “no”). If you are currently feeling the worst discomfort possible, you should circle the vertical line on the right end of the scale.

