About how long did the nausea last? (please approximate the number of minutes of nausea out of the prior 6 hours)

_____ (minutes)

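### Appendix D's site instructions define the single BARF/VAS mark both as the 6-hour worst and as the discomfort remaining at the rating, and its duration item times nausea only

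*Combined protocol and SAP*

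**What the plan says.** The Endpoints section lists the BARF/VAS score after each meal, and the mean duration of gastrointestinal issues reported on the same form, as safety endpoints. The Study Hypothesis includes good tolerability.

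Under Meal Description, both the insulin visit and the insulin + pramlintide visit have the participant complete the scale about 6 hours after each meal "to report the worse nausea/vomiting they experienced over the prior 6 hours".

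In Protocol Appendix D, the Investigative Site Instructions have the form completed "to indicate the worse nausea/vomiting discomfort they have had over the prior 6 hours". The same block tells staff: "Instruct the participant that the facial expressions represent the nausea severity they are experiencing". After describing how the line is drawn, it adds: "The goal is for the subject to report the amount of discomfort, if any, remaining at each time point".

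The Subject Instructions say that a mark further to the right means "the more intense discomfort you are feeling". They then give the main rule: "You should normally draw a straight line across the scale to indicate your maximum level of discomfort over the prior 6 hours". The left end is for a participant who felt no discomfort (past tense). For the right end: "If you are currently feeling the worst discomfort possible, you should circle the vertical line on the right end of the scale".

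The form ends with a duration question on nausea: "please approximate the number of minutes of nausea out of the prior 6 hours".

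**The concern.** A peak over 6 hours and a residual at hour 6 are different quantities, and the participant draws only one line per rating. The form therefore cannot record both, and no text says which definition prevails. Six hours leaves time for a post-meal episode to pass, so the two definitions can give very different scores for the same person.

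At stake is the participant-reported severity that informs tolerability. The risk section says that pramlintide can cause nausea and rates this as somewhat likely. If nausea is more frequent at the pramlintide visit, scoring some resolved episodes low would shrink the difference between visits. Using the same form at both visits does not cancel this. The staff who explain the form would also know the treatment: the visits use one pod and two pods respectively, and the text describes no masking.

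A second, separate problem is scope. Severity and duration are collected on one form but do not cover the same symptoms.

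**Working it through.** The plan states no figure on this point, so there is none to reproduce. The check is a comparison of texts, followed by an illustration of size.

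**1. What each instruction measures**

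| Place | Quantity |
|---|---|
| Meal Description, insulin visit | 6-hour worst |
| Meal Description, insulin + pramlintide visit | 6-hour worst |
| Appendix D, site instructions, opening | 6-hour worst |
| Appendix D, site instructions, meaning of the faces | present tense |
| Appendix D, site instructions, stated goal | discomfort remaining at the rating |
| Appendix D, participant text, meaning of the scale | present tense |
| Appendix D, participant text, main rule | 6-hour maximum |
| Appendix D, participant text, left end | past tense, no window stated |
| Appendix D, participant text, right end | current state |

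The 6-hour worst appears four times. The direct conflict lies within the site instructions, between the opening and the stated goal.

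**2. Direction.** The discomfort remaining at hour 6 cannot exceed the maximum over a window that ends at hour 6. Any switch from worst to remaining therefore leaves the score unchanged or lowers it. As a hypothetical case, an episode that peaked at 60 mm and had gone by the rating scores 60 on one definition and 0 on the other.

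**3. Route to a zero.** The left end applies to someone who felt no discomfort, and a participant who was nauseated and recovered does not fit that description. The word for the current state occurs only at the right end. There it could keep someone whose worst-possible episode has passed from circling that end, but it does not direct anyone to zero. A zero for a resolved episode thus arises mainly when staff explain the form by its stated goal.

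**4. Size.** Let r be the fraction of episodes resolved by the rating and m the fraction of those rated as of now. Neither is in the documents; both ranges below are assumed.

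- Share of episodes scored zero = r × m.
- Low end: 0.5 × 0.25 = 12.5%. High end: 0.9 × 1.0 = 90%.
- With the planned 35 participants and an assumed 30% with nausea, 35 × 0.30 = 10.5 are expected to have an episode. Recorded as non-zero: 10.5 × (1 − 0.125) = 9.2 at the low end and 10.5 × (1 − 0.90) = 1.05 at the high end.
- If resolved and unresolved episodes have comparable peaks, the mean score among symptomatic participants falls by at least r × m. At m = 0.5 that is 25% for r = 0.5 and 45% for r = 0.9.

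The width of the range shows that the documents do not fix the size.

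**5. Symptom scope.** The participant text counts cramps, abdominal pain, nausea and vomiting as discomfort. The duration question counts minutes of nausea. The endpoint is the duration of gastrointestinal issues. A participant with cramps alone has a severity score and no duration to report.

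**The case against.** The strongest reply is that a reader would rarely be misled. The 6-hour worst is the rule in both visit sections, in the opening of Appendix D and in the main participant instruction. The goal of recording what remains appears once, in text addressed to sites. The other present-tense phrases are loose wording and, in the participant text, the explicit 6-hour rule follows directly. This stands, and it limits the point to a conflict in the site instructions plus a misworded right anchor.

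A reader might infer that participants themselves are told to score a resolved episode as zero. The documents do not support that: the left end is in the past tense and the main rule is the maximum.

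A reader might also infer that nausea from pramlintide would be hidden. That is too strong. The duration item looks back over the full 6 hours, adverse events (including those possibly or probably associated with pramlintide) are separate safety endpoints, and staff stay near the participant throughout. The cross-check is only partial, however. The duration item misses symptoms other than nausea, the plan specifies no query for zero severity with non-zero minutes, and neither source restores a peak that was not marked.

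It is also fair to say that no planned inference depends on the score. The Statistical methods section sets no tolerability test or threshold.

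The printed scale is not shown in the available text, so its own anchor labels could not be checked.

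**Conclusion.** Wrong as written, and minor. Appendix D gives one mark two incompatible definitions, and its duration item is narrower than both the severity item and the endpoint it feeds. Followed literally, the form can mis-measure two listed safety endpoints. The severity error can only go downwards. The primary endpoints, iAUC and time in range, are untouched.

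The size is unknown. The 12.5% to 90% range rests wholly on assumed values of r and m. One might be tempted to say that the mean score among symptomatic participants would be halved if half of those with resolved symptoms rated the present moment. That holds only if every symptomatic participant has resolved by hour 6 (r = 1), which nothing in the documents states.

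A reader might also count it as an error that Appendix D does not list the study-start rating. Both visit sections already require that rating, so this is an omission and not a contradiction. No change-from-baseline analysis is planned that would need it.

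**What to change.** Make three edits to Appendix D:

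1. Delete the site-instruction sentence about discomfort remaining at each time point.
2. Reword the present-tense phrases (what the faces represent, what a mark further to the right means) and the right anchor so that all refer to the worst discomfort over the prior 6 hours.
3. Make the duration item ask about the same symptoms as the severity item, which also matches the endpoint.

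The cost is a few words on one form and a minor amendment, with no added visits or procedures. The change should come before further forms are completed, because a peak that was not marked cannot be recovered from the score.

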- Net area under the curve (netAUC) of postprandial glucose as measured by CGM in the 6 hours following the start of first meal. netAUC (mg/dL*min) will be calculated using a trapezoidal method [76], which sums all CGM values in the 6 hour period following the meal above the starting glucose and subtracts CGM values below the starting glucose.
- Percent of time with sensed glucose <70 mg/dl
- Percent of time with sensed glucose between 70 – 140 mg/dl
- Mean sensed glucose
- Percent of time with sensed glucose <54 mg/dl
- Percent of time with sensed glucose >180 mg/dl
- Percent of time with sensed glucose >250 mg/dl
- Mean amount of insulin delivered (in units and units/kg)
- Mean amount of pramlintide delivered (in mcg and mcg/kg)
- Coefficient of variation
- LBGI
- HBGI
- Safety endpoints (over full study duration):
 - Adverse events
 - Number of adverse events probably or possibly associated with pramlintide administration (see ‘Causality Relationship’ below)
 - Baxter Retching Faces (BARF)/VAS scale for gastrointestinal issues after first and second meal, see Protocol Appendix D.
 - Mean duration of gastrointestinal issues after first and second meal as reported by participant on BARF/VAS scale, see Protocol Appendix D.
 - Episodes of carbohydrate intake to treat hypoglycemia (defined as 15g carbohydrate intake)
 - Episodes of hypoglycemia defined as CGM <70mg/dL for 10 minutes or more
 - Number of provider-administered insulin injections due to hyperglycemia

Study Type

This is a single-center, crossover trial designed to evaluate glucose outcomes of a fully closed-loop system with insulin+pramlintide dosed in response to meal detection as compared to an insulin alone fully closed loop system.

Study Population

Study population will be adults with type 1 diabetes, ages 18 – 70 years of age. Younger participants are excluded as it is appropriate to assess safety first in the over 18 year old population. We are targeting a total of 35 participants to complete the full study protocol.

[figure not shown]
Power Analysis

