When either the CGM or the insulin pump is out for the above time durations, the iPancreas system will activate a predictive low glucose suspend feature if the last known sensor value was within the range of 70-140 mg/dl and predicted to fall below 90 mg/dl within thirty minutes or if the sensor glucose is less than 70 mg/dl. Maximum insulin suspension time is 2 hours. Prediction of sensor glucose is based on data long short term memory neural network (LSTM) algorithm[77]. When communication with the sensor or Omnipod is restored, the system will automatically resume delivering insulin according to the control algorithm, and IOB will be updated accordingly.

Meal Description

After the closed loop study has started, participants will eat the assigned breakfast meal around 8am. The assigned lunch meal will be given six hours later around 2 pm. The meal time may be delayed for safety if participant had a recent low glucose. The selected breakfast and lunch option will be identical across both study arms for each participant. The participant will be requested to complete their meal within 10 minutes. There will not be a premeal insulin bolus.

The participant will select between two or three breakfast and lunch meals options and have these same meals at each study visit. If a food item is unavailable, it will be substituted with the closest available substitute. The caloric size of the meal will be based on DRI Estimated Energy

requirement formulas. The meals will be made by the OHSU Bionutrition kitchen. The breakfast meal options will each provide approximately 33% of participants daily energy requirement, with macronutrient composition of 50% carbohydrate, 15% protein and 35% fat. The lunch meal options will provide approximately 40% of the participants daily energy requirement with the same macronutrient composition as the breakfast meal.

Meal detection will be enabled for the study. If iPancreas does not auto-detect the meal after 30 minutes of when they start eating, the study coordinator will assist the participant to enter a meal with the amount of carbs provided by Bionutrition. Participants will complete a pictorial nausea rating scale for reported nausea at study start and at approximately 6 hours after the first and second meal to report the worse nausea/vomiting they experienced over the prior 6 hours (the Baxter Retching Faces [BARF] scale) (see Protocol Appendix D)[78] and the approximate duration of the nausea.

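### The safety endpoint is the duration of gastrointestinal issues, but the form and both visit procedures collect only minutes of nausea

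*Combined protocol and SAP*

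**What the plan says.** The safety list under Secondary Endpoints has two items from the nausea form. One is severity: "Baxter Retching Faces (BARF)/VAS scale for gastrointestinal issues after first and second meal". The other is time: "Mean duration of gastrointestinal issues after first and second meal as reported by participant on BARF/VAS scale". Both are worded for GI issues in general, and both point to Protocol Appendix D.

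Appendix D tells the participant what to count when marking severity: "Discomfort could include cramping, abdominal pain, nausea or vomiting". The instruction to site staff is narrower: "Instruct the participant that the facial expressions represent the nausea severity they are experiencing". The form then has a single duration question, "About how long did the nausea last", with the gloss "please approximate the number of minutes of nausea out of the prior 6 hours" and a blank for the minutes.

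The Meal Description sections of the Insulin Treatment Visit and the Insulin + Pramlintide Treatment Visit describe the same data collection. After the severity rating, each adds "and the approximate duration of the nausea".

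The same endpoint list also has adverse events and, separately, "Number of adverse events probably or possibly associated with pramlintide administration".

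**The concern.** The endpoint covers several symptoms, and its only data source asks about one of them. A participant who had cramps but no nausea can mark high severity and, answering the next question correctly, report no minutes. If the plan is followed as written, minutes of nausea will be reported under the label of GI duration.

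This matters because the Study Hypothesis includes good tolerability and the first primary objective includes safety. The severity score and the duration are the only scaled GI measures in the endpoint list. Minutes that were never asked for cannot be rebuilt from this form at analysis.

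**Working it through.** There is no planned figure to reproduce, because the documents give no expected duration, symptom rate or scoring rule for this endpoint. The check is a comparison of texts, followed by an illustration under stated assumptions.

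**Symptoms covered, place by place**

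| Place | What is measured | Symptoms covered |
|---|---|---|
| Secondary Endpoints, safety list | Severity | GI issues |
| Secondary Endpoints, safety list | Duration | GI issues |
| Appendix D, participant instruction | Severity | Cramps, abdominal pain, nausea, vomiting |
| Appendix D, site instruction | Severity | Nausea and vomiting; the faces stand for nausea |
| Appendix D, duration question | Duration | Nausea |
| Meal Description, both visits | Duration | Nausea |

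For duration, every collection step says nausea and only the endpoint label says GI issues. No other section names a source for the duration of non-nausea symptoms. An adverse event form is listed under Recording of Data, but the documents do not say that it records start and stop times or that it feeds this endpoint.

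**What happens to a meal period with symptoms but no nausea**

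Let q be the share of such periods in an arm, m their mean true duration, and a the mean duration over all other periods. For simplicity, suppose that nausea minutes equal GI minutes in those other periods. The true mean is (1 − q)a + qm. No scoring rule is given, so three outcomes are possible:

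- Entered as zero: the recorded mean is (1 − q)a, a shortfall of qm.
- Left blank and dropped: the recorded mean is a. The error is a − [(1 − q)a + qm] = q(a − m), an understatement only if m is larger than a.
- Answered for all the discomfort just rated: no error.

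Periods with both nausea and other symptoms at different times lose minutes too, so the zero-entry shortfall is not an upper limit.

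**Illustration for zero entry (q and m are assumptions, not taken from the documents)**

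| q | m = 30 min | m = 60 min | m = 120 min |
|---|---|---|---|
| 5% | 1.5 | 3 | 6 |
| 10% | 3 | 6 | 12 |
| 20% | 6 | 12 | 24 |

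Each cell is q × m, the shortfall in minutes per meal period in one arm.

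**Effect on the comparison**

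With zero entry, the understatement of the difference (insulin + pramlintide minus insulin alone) is q_pram × m_pram − q_ins × m_ins. If the products are equal, it is zero. With m = 60 in both arms, q = 20% on the combination and 5% on insulin alone, it is 12 − 3 = 9 minutes in favour of the combination. The documents supply none of these four quantities.

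**The case against.** The strongest reply is that the form asks about the effect that matters. The Risks section names nausea, and less often vomiting, as the GI effects of pramlintide; it mentions neither cramps nor abdominal pain. The procedures and the form agree with each other on duration, so the endpoint label may simply be loose wording for nausea. Other symptoms are not invisible: the participant instruction admits them to the severity mark, adverse events and their relation to pramlintide are endpoints of their own, and staff stay near the participant throughout.

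Most of this stands, and it limits the point. It does not remove it: none of these routes is stated to give minutes of non-nausea symptoms. The severity mark is also an imperfect backstop, since staff and participant are told different things about what it covers. How far that conflict shows on the actual form cannot be judged, because the faces figure is not available.

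A reader might go further and infer that symptoms without nausea score zero and that tolerability of the combination is therefore overstated. The documents do not support that. No scoring rule produces a zero. Only the duration item is affected. The same form is used at both visits, so bias between arms needs a difference in non-nausea time. The Risks section makes such a difference plausible for vomiting, since it lists no GI effect for insulin, but it puts no number on it.

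**Conclusion.** The mismatch is certain from the text: the duration endpoint as named cannot be measured with its named form, because time with cramps, pain or vomiting in the absence of nausea is not asked for. Read literally, GI duration may be understated. The size is unknown; the range of 1.5 to 24 minutes per meal period rests wholly on the assumed q and m and on zero entry. Neither a bias between arms nor an overstatement of tolerability in general is shown.

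This is a secondary safety endpoint. The primary endpoints, the sample size and the primary analysis are untouched. It is still worth correcting, because the change is small and the missing minutes cannot be recovered from this form.

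**What to change.** Choose one of two routes.

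1. **Keep the GI endpoint.** Reword the duration question to ask for the minutes, out of the previous six hours, with any of the discomforts listed for the severity mark. Nausea minutes can stay as a second line. Align the Meal Description of both treatment visits and the site instruction in Appendix D with the same symptom list.
2. **Keep the form.** Rename the duration endpoint to duration of nausea, which already matches the form and both procedures, and limit the conclusion on duration to nausea.

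Under either route, state how a period with symptoms but no nausea is to be recorded, and distinguish zero from blank.

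The second route costs one line of endpoint wording plus the recording rule. The first needs small edits in the form, the site instruction and both visit procedures. Forms completed before a change to the question must be flagged, because their minutes refer to nausea only.
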